## **2.1 Primary objective**

To assess the frequency of use of objective neuromuscular monitoring with acceleromyography in 7 Danish anaesthesia departments, using 18 months of retrospectively collected data from the Anaesthesia Information Management System (AIMS).

## **Secondary objectives**

To assess the incidence of residual neuromuscular blockade, the frequency and timing of reversal of the neuromuscular blockade with sugammadex or neostigmine, and the association between hypoxemic events and use of neuromuscular monitoring.

### **2.1.1 Clinical hypotheses**

We hypothesize that objective neuromuscular monitoring is applied in 80% of cases involving a non-depolarizing NMBA (with or without succinylcholine) and 50% of cases involving only succinylcholine.

## **Perspectives**

Unlike in the U.S. and many European countries, most Danish operating rooms are equipped with objective neuromuscular monitoring. However, it is not known to which degree the equipment is actually being used, which will be investigated in this study. Moreover, the study will serve as a baseline study for a future interventional study with the aim of increasing the use of objective neuromuscular monitoring.

---

Neuromuscular blocking agents (NMBAs) are used in general anaesthesia to facilitate endotracheal intubation and improve surgical conditions. Postoperative residual neuromuscular blockade occurs if the effects of the NMBA have not subsided or been sufficiently reversed when the patient is awakened. Residual neuromuscular blockade is associated with both subjective complaints such as general fatigue, double vision and difficulty of speech, as well as increased risk of respiratory complications and prolonged length of stay in the post-anaesthesia care unit (PACU). A peripheral nerve stimulator applied intra-operatively allows for assessment of the degree of neuromuscular blockade. Objective neuromuscular monitoring, combining the peripheral nerve stimulator with measuring the response to nerve stimulation by means of e.g. acceleromyography, allows for more precise determination of the depth of neuromuscular blockade. The use of objective neuromuscular monitoring may prevent or reduce the incidence of residual neuromuscular blockade. Routine use of objective neuromuscular monitoring is recommended whenever administering intermediate-acting, i.e. non-depolarizing, NMBAs. We have showed

that patients receiving short-acting NMBAs also risk experiencing being awake while paralysed, especially if not monitored with a nerve stimulator. Hence, it has recently been recommended that objective neuromuscular monitoring should be applied whenever any type of NMBA is administered. In a Danish survey from 2005, 43% of anaesthetists replied that they always use neuromuscular monitoring when administering an NMBA. However, the actual frequency of application of neuromuscular monitoring and the incidence of residual neuromuscular blockade is not known.

The study is a cross-sectional study with data from anaesthesia departments of seven Danish teaching hospitals in the Zealand Region of Denmark. The departments use the same objective neuromuscular monitoring device integrated in the anaesthesia machine (Philips MP70 NMT module (acceleromyography)) and the same AIMS (Metavision Anaesthesia (iMDsoft , Germany)).

### **Eligibility**

We will include all patients who received general anaesthesia with neuromuscular blockade in the 18 months up until the time of data collection. Patients, who are eligible more than once, i.e. undergoing general anaesthesia on more than one occasion, will be included in the analyses as a case for every general anaesthetic received.

### **Primary outcomes**

- Proportion of cases involving a non-depolarizing NMBA (with or without succinylcholine) where objective neuromuscular monitoring is applied.
- Proportion of cases involving only succinylcholine where objective neuromuscular monitoring is applied.

The primary outcome is split in cases with non-depolarizing NMBAs and cases with succinylcholine only, as the types of NMBAs are typically used in different clinical situations, i.e. for non-emergent tracheal intubation and rapid sequence induction, respectively.

### **Secondary outcomes**

- Median of last recorded TOF ratio before tracheal extubation or removal of supraglottic airway device in patients receiving a non-depolarizing NMBA.
- Proportion of cases involving a non-depolarizing NMBA receiving sugammadex or neostigmine, respectively.
- Proportion of cases involving a non-depolarizing NMBA receiving more than one administration of a reversal agent.
- Timing of NMBA reversal with sugammadex or neostigmine, respectively, according to an ordinal scale (neostigmine: TOF count 0, 1, 2, 3, [TOC count 4 to TOF ratio 0.9], TOF ratio  $\geq 0.9$ ) (sugammadex: PTC 0, PTC 1 to 15, TOF 0, 1, 2, 3 [TOC count 4 to TOF ratio 0.9], TOF ratio  $\geq 0.9$ ).
- Proportion of cases receiving an NMBA before tracheal intubation.
- Proportion of cases involving a non-depolarizing NMBA in which neuromuscular monitoring was applied before tracheal intubation.
- Time from tracheal extubation or removal of supraglottic airway device to discharge from PACU in cases involving a non-depolarizing NMBA with and without neuromuscular monitoring, respectively.

- Proportion of cases involving a non-depolarizing NMBA with mild oxygen desaturation (<90%) in the time between tracheal extubation or removal of supraglottic airway device and discharge from PACU with and without neuromuscular monitoring, respectively.
- Proportion of cases involving a non-depolarizing NMBA with severe oxygen desaturation (<80%) in the time between tracheal extubation or removal of supraglottic airway device and discharge from PACU with and without neuromuscular monitoring, respectively.

All outcomes will be reported both as total and for each department separately, as well as for 3-month periods.

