### **Data collection**

Data are recorded in the AIMS in two ways: automatically or manually by the anaesthetist. Automatically recorded data include respiratory parameters like peripheral oxygen saturation as well as TOF data. Manually entered data include type and dose of intravenously administered medication and time of tracheal extubation. TOF data are recorded automatically when the neuromuscular monitoring module is activated. The AIMS saves automatically recorded TOF data every minute, that is, even though the neuromuscular monitoring module may be set to measure a TOF value every 12 s, data will only be stored once every minute. To ensure that the reported TOF values at tracheal extubation are not erroneously measured due to e.g. lack of fixation of the patient's hand or movements caused by the surgical personnel, we will collect the last five TOF values before tracheal extubation and use the highest value. In cases with desaturation, the electronic anaesthesia chart including the anaesthetist's comments will be reviewed to confirm the event.

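### Recovery at extubation is summarised as a median TOF ratio, which gives no place to cases last seen at TOF count 0 to 3

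*Protocol*

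**What the plan says.** Protocol, Secondary outcomes, defines recovery at the end of anaesthesia as the "Median of last recorded TOF ratio before tracheal extubation or removal of supraglottic airway device in patients receiving a non-depolarizing NMBA". No other listed outcome describes recovery at that moment.

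The same list grades the timing of reversal on an ordinal scale. For neostigmine it runs "neostigmine: TOF count 0, 1, 2, 3, [TOC count 4 to TOF ratio 0.9], TOF ratio" of 0.9 or more, so counts 0, 1, 2 and 3 are separate levels and the ratio enters only from count 4 upward. The sugammadex scale has the same count levels, with post-tetanic counts below them.

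Data collection adds a rule for the value at extubation: "we will collect the last five TOF values before tracheal extubation and use the highest value". It also states that "data will only be stored once every minute" and that "TOF data are recorded automatically when the neuromuscular monitoring module is activated".

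Secondary objectives begins "To assess the incidence of residual neuromuscular blockade".

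**The concern.** The protocol recognises states of block too deep to have a ratio and expects to find them in the AIMS, yet it measures recovery on a scale that starts above them. A case whose readings up to extubation are counts of 0 to 3 has no ratio at that point. Followed as written, the outcome either omits the case or uses an older ratio from a time when four twitches were present.

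The cases affected are chosen by the outcome itself, since they have the deepest recorded block. They are also the cases that the residual-blockade objective is about. All outcomes are to be reported by department and by 3-month period, so a varying share of such cases would distort those comparisons as well. The Perspectives section makes the study a baseline for a later interventional study.

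**Working it through.** **No figure to reproduce.** The protocol gives no expected TOF ratio, sample size or precision for this outcome. The check is a reading of the text followed by rank arithmetic.

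**Does Data collection close the gap?** There are two readings of its TOF values.
- If they are ratios, the last five ratios can reach back past a run of counts. At one stored value per minute, five consecutive values span 4 intervals, or 4 minutes, but only if the module runs without gaps and every reading is a ratio. No time limit is set.
- If they include counts, a count of 3 and a ratio of 0.7 are on different scales, and the highest is undefined until an order is given.

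The gap stays open on either reading.

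**Can an early ratio be in the record?** Data are stored whenever the module is active, and one outcome is the "Proportion of cases involving a non-depolarizing NMBA in which neuromuscular monitoring was applied before tracheal intubation". Early readings can therefore exist, possibly from before the NMBA. For such a ratio to represent the case at extubation, there must be no later ratio, or fewer than five later ones under the highest-of-five rule.

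**Rank arithmetic.** Let p be the share of monitored cases last seen at count 0 to 3. It is assumed, as the documents do not give it.
- Dropped: the reported median is the p + (1 − p)/2 = (1 + p)/2 quantile of all monitored cases. For p = 5%: 1.05/2 = 52.5th percentile. For p = 10%: 1.10/2 = 55th.
- All carried at a baseline ratio near 1.0 (upper bound): the reported median is the 0.5 + p quantile, so the 55th and 60th percentiles.

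**Size on the ratio scale.** This was simulated with 400,000 cases. The ratios of the other cases were assumed to follow Beta(18,2) or Beta(9,1.5). Ranked means counts 0 to 3 lie below every ratio. The cut at 0.9 is the top boundary of the protocol's scale and is used only for illustration; the protocol does not define residual blockade by it.

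| Ratios | p | Median: ranked / dropped / carried | Share below 0.9: ranked / dropped / carried |
|---|---|---|---|
| Beta(18,2) | 1% | 0.912 / 0.913 / 0.914 | 42.6% / 42.0% / 41.6% |
| Beta(18,2) | 5% | 0.909 / 0.913 / 0.917 | 44.9% / 42.0% / 39.9% |
| Beta(18,2) | 10% | 0.904 / 0.913 / 0.922 | 47.8% / 42.0% / 37.8% |
| Beta(9,1.5) | 1% | 0.879 / 0.880 / 0.881 | 58.7% / 58.3% / 57.7% |
| Beta(9,1.5) | 5% | 0.873 / 0.880 / 0.887 | 60.4% / 58.3% / 55.4% |
| Beta(9,1.5) | 10% | 0.866 / 0.880 / 0.894 | 62.5% / 58.3% / 52.5% |

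The shares can be checked by hand. If s is the share below 0.9 among cases with a ratio, the ranked share is p + (1 − p)s. For Beta(18,2) at 5% this is 0.05 + 0.95 × 0.420 = 0.449.

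For p of 5% to 10%, dropping cases raises the median by 0.004 (0.913 − 0.909) to 0.014 (0.880 − 0.866). It lowers the share below 0.9 by 2.1 points (60.4 − 58.3) to 5.8 points (47.8 − 42.0). At 1% the median moves by about 0.001.

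**The case against.** The strongest reply is that coding of readings below count 4 belongs in the SAP or a data dictionary, and that the protocol nowhere says such cases are excluded. If the AIMS stores a ratio of 0 for them, they stay in. This limits the point but does not remove it. The protocol itself fixes both the scale and the selection rule, so a SAP that ranked counts below ratios would be changing the outcome as worded. Even with stored zeros, the highest-of-five rule could replace a 0 with an earlier ratio.

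A second reply is that the Data collection text speaks of TOF values, not ratios, so a case with five counts could stay in as a low value. That reading is possible, but it supplies no order between counts and ratios.

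Three stronger claims are tempting and not supported.
- A reader might infer that deeply blocked cases will be scored at their pre-NMBA baseline. The quoted outcome concerns monitoring before intubation, which may still be after the NMBA, and the route needs few or no later ratios. Moving the whole share p to the top is therefore an upper bound.
- A reader might infer that reported recovery is always better than true recovery. A last recorded count is not always the state at extubation: if the module was switched off after reversal, the patient may have recovered unrecorded. The direction is certain only relative to the recorded readings.
- A reader might take the percentile shifts as large errors in the median. On the ratio scale they are small.

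**Conclusion.** The point holds as a defect in the outcome definition. The ratio-only outcome does not fit the protocol's own scale, and the highest-of-five rule does not repair it. The effect on the median is small: 0.004 to 0.014 under the assumed distributions with 5% to 10% of cases dropped, and negligible at 1%. The more serious effect is on the residual-blockade objective, whose only outcome at extubation can leave out the cases with the deepest recorded block.

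This rests on two things the documents do not give: that the AIMS does not store a ratio of 0 for counts below 4, and that the share of such cases is not trivial.

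**What to change.** Reword the outcome so that the highest-of-last-five rule applies to all stored TOF readings, ordered as in the reversal-timing scale with counts 0 to 3 below every ratio. This keeps the protocol's safeguard against artefacts and makes highest well defined. Use only readings after the first NMBA dose, and state how the AIMS stores the ratio when the count is below 4.

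Report the number and proportion of cases at count 0 to 3 beside the median. Also report the time from the last reading to extubation or device removal, so that a case whose monitor was switched off early is not read as blocked at extubation. Without this, ranking the counts lowest could overstate residual block.

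The cost is outcome wording and one recoding step in data taken from the AIMS, with no additional patients. Reported recovery may look slightly less favourable.

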### **Data collection**

Data are recorded in the AIMS in two ways: automatically or manually by the anaesthetist. Automatically recorded data include respiratory parameters like peripheral oxygen saturation as well as TOF data. Manually entered data include type and dose of intravenously administered medication and time of tracheal extubation. TOF data are recorded automatically when the neuromuscular monitoring module is activated. The AIMS saves automatically recorded TOF data every minute, that is, even though the neuromuscular monitoring module may be set to measure a TOF value every 12 s, data will only be stored once every minute. To ensure that the reported TOF values at tracheal extubation are not erroneously measured due to e.g. lack of fixation of the patient's hand or movements caused by the surgical personnel, we will collect the last five TOF values before tracheal extubation and use the highest value. In cases with desaturation, the electronic anaesthesia chart including the anaesthetist's comments will be reviewed to confirm the event.

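### Desaturation is confirmed by chart review and then compared by monitoring status; masking the reviewer to TOF data and reporting results before and after review would be a cheap safeguard

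*Protocol*

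**What the plan says.** Three parts of the protocol bear on this.

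- **Source data (Data collection).** "Automatically recorded data include respiratory parameters like peripheral oxygen saturation as well as TOF data". On the exposure: "TOF data are recorded automatically when the neuromuscular monitoring module is activated". Saturation and TOF values therefore sit in the same anaesthesia information system, and stored TOF values mark a case as monitored.
- **Confirmation (Data collection, last sentence).** "In cases with desaturation, the electronic anaesthesia chart including the anaesthetist's comments will be reviewed to confirm the event". The sentence fixes the source (chart and comments) and the purpose (confirmation). It does not say what the reviewer is shown.
- **Use (Secondary objectives; Secondary outcomes).** One objective is to assess "the association between hypoxemic events and use of neuromuscular monitoring". Mild (<90%) and severe (<80%) desaturation are each counted from extubation or "removal of supraglottic airway device and discharge from PACU with and without neuromuscular monitoring, respectively". The thresholds and the time window are thus already fixed.

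The background under Perspectives states an expectation: "The use of objective neuromuscular monitoring may prevent or reduce the incidence of residual neuromuscular blockade". It also links residual blockade to respiratory complications, and describes the study as a baseline for later work meant to raise the use of monitoring.

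**The concern.** An automatically recorded measurement becomes an outcome only after a person has read the chart, and the groups then compared are defined by something that may be visible on that chart. A reviewer who knows the group, and who has read the background to this study, could be readier to accept or to dismiss a low reading in one group than in the other. Any such difference would pass straight into the two desaturation comparisons, and the protocol at hand does not provide for the counts that would let a reader see it.

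The two desaturation outcomes, and the secondary objective they serve, are what is at stake. The two primary outcomes (proportions monitored) and the other seven secondary outcomes do not pass through this review.

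**Working it through.** The protocol gives no number of cases, event rate or rejection rate for these outcomes, so there is no stated figure to reproduce. The check asks how differential rejection would act on the comparison.

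**1. The factor.** In each group, let *f* be the proportion of cases flagged from the automatic record and *r* the share of flagged cases rejected at review. The confirmed proportion is *f*(1 − *r*), so

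confirmed RR = flagged RR × (1 − *r* if monitored)/(1 − *r* if unmonitored).

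- Equal rejection gives a factor of 1. Reviewing only flagged cases is therefore not in itself a fault: it lowers both proportions but leaves their ratio unchanged.
- If rejection differs because truly erroneous readings are commoner in one group, the factor is a correction. It is a bias only where rejection differs for other reasons.

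**2. Illustrative sizes, no true difference and equal flagging (rejection rates assumed).**

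| Rejected if monitored | Rejected if unmonitored | Factor |
|---|---|---|
| 30% | 30% | 0.70/0.70 = 1.00 |
| 35% | 30% | 0.65/0.70 = 0.929 |
| 37% | 30% | 0.63/0.70 = 0.900 |
| 20% | 10% | 0.80/0.90 = 0.889 |
| 30% | 38% | 0.70/0.62 = 1.129 |

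The last row shows that the distortion can run in either direction.

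**3. Could it produce a false association?** Take 80% monitored (the hypothesis in 2.1.1 for non-depolarizing agents). Assume 15% flagged, 20,000 cases, and rejection of 35% against 30%.

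- Confirmed proportions: 0.15 × 0.65 = 0.0975 of 16,000 (1,560 events) and 0.15 × 0.70 = 0.105 of 4,000 (420 events).
- SE(log RR) = √[(1 − 0.0975)/1,560 + (1 − 0.105)/420] = 0.052.
- RR 0.929, 95% CI 0.838 to 1.028; |log RR|/SE = 0.0741/0.0521 = 1.42.
- Chance of two-sided p < 0.05: Φ(1.42 − 1.96) ≈ 30%, although this particular interval includes 1.

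With the same formula and the same 5-point gap, the chance is about 11% with 5,000 cases and 61% with 50,000.

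**4. Why no threshold can be given.** With 15% flagged and 30% rejected if unmonitored, the smallest whole-percent rejection if monitored at which the interval excludes 1 is:

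| Cases (assumed) | Rejection if monitored | Gap |
|---|---|---|
| 5,000 | 44% | 14 points |
| 20,000 | 37% | 7 points |
| 50,000 | 35% | 5 points |
| 100,000 | 34% | 4 points |

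These are roughly the gaps at which a false positive is as likely as not. Smaller gaps are not safe, as step 3 shows. Rarer events need wider gaps: with 2% flagged and 20,000 cases the figure is 49%, a gap of 19 points.

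**5. Dependence between cases.** Patients may contribute several anaesthetics (Eligibility) and cases come from seven departments. If the variance were doubled (an assumption), the ratio in step 3 becomes 1.42/√2 = 1.01 and the chance falls from about 30% to about 17%. The factor in step 1 does not change.

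**The case against.** The strongest reply is that this is silence, not error. The protocol names the source for the review but does not say that the review is unmasked or without rules. Masking, or a rule for erroneous readings, may stand in an analysis plan or review manual that is not shown, and nothing in the sentence prevents either. Bias also needs a chain that the text does not establish: the reviewer sees TOF data, holds an expectation, lets it affect rejection, and does so differently by group. The event window begins at airway removal, while the TOF values collected for the extubation outcome come before it, so checking a saturation value need not involve the TOF record.

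Much of this stands. A reader might infer that the protocol plans subjective, unmasked adjudication, that it leaves artefact to the reviewer's discretion, or that the comparison is tilted in favour of monitoring. The document supports none of these. It discusses erroneous measurement only for TOF values, does not describe the chart display, and gives no ground for a direction.

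What survives is narrower. The protocol itself fixes this confirmation step, as part of data collection and not as an analysis detail. The source it names may reveal the exposure being compared. The stated method can be made safer at little cost without altering any definition.

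**Conclusion.** The point holds as a minor, cheap improvement to two of the nine secondary outcomes. That the chart may reveal monitoring status is an inference from saturation and TOF data being held in one system. No bias is demonstrated, and its size and direction cannot be known from the protocol. Its mechanism can be stated exactly: any difference in rejection not due to true error multiplies the risk ratio by (1 − rejection if monitored)/(1 − rejection if unmonitored).

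A reader might take the figures in the working as a tolerance below which differential rejection is harmless. They are not. Apart from the 80% hypothesis, every input is assumed, and the gap that matters shrinks as the number of cases grows.

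Nor would masking make the desaturation comparison causal: who is monitored was not randomised, and that confounding remains whatever is done at review.

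**What to change.** Replace the last sentence of Data collection with:

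> Cases with desaturation will be reviewed, including the anaesthetist's comments, from an extract without TOF data and by a reviewer not told monitoring status; the <90% and <80% definitions do not change. Numbers flagged and rejected will be reported by monitoring status, and both desaturation proportions will be given before and after review.

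The review is already planned, so the added cost is some work to prepare the extract and to tabulate the counts. If an analysis plan or manual already provides for this, a cross-reference is enough.

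Two limits should be accepted openly. Masking may be incomplete where comments mention monitoring. The proportions before review still contain erroneous readings, so a gap between the two sets of results signals a question without showing which set is right.
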